25. Have significant active cardiac disease within 6 months prior to the start of study treatment, including New York Heart Association (NYHA) Class III or IV congestive heart failure ([Appendix 11](#)); myocardial infarction; unstable angina; and/or stroke.
26. Have LVEF $<$ 40% by ECHO scan (or by other methods according to institutional practice) obtained within 28 days prior to the start of study treatment.
27. Have a heart-rate corrected QT interval (using Fridericia's formula) (QTcF) ([Appendix 8](#)) \geq 450 msec or other factors that increase the risk of QT prolongation or arrhythmic events (eg, heart failure, hypokalemia, family history of long QT interval syndrome). Bundle branch block and prolonged QTcF interval are permitted with approval of the Sponsor.
28. Are taking medications that are known to prolong the QT interval ([Appendix 9](#)) unless they can be transferred to other medications within \geq 5 half-lives prior to dosing or unless the medications can be properly monitored during the study. (If equivalent medication is not available, QTcF should be closely monitored.)
29. Have known active hepatitis B (HBV) or hepatitis C (HCV) infections, known positive human immunodeficiency virus (HIV) antibody results, or acquired immunodeficiency syndrome (AIDS)-related illness. Subjects with a sustained viral response to HCV treatment or immunity to prior HBV infection will be permitted. Subjects with chronic HBV that is adequately suppressed per institutional practice will be permitted.
30. Have any other acute or chronic medical or psychiatric condition, including recent (within 12 months of Day 1) or active suicidal ideation or behaviour, or a laboratory abnormality that may increase the risk associated with study participation or investigational product administration or may interfere with the interpretation of study results and, in the judgment of the Investigator, would make the subject inappropriate for entry into this study.
31. Have known active inflammatory gastrointestinal disease, chronic diarrhoea, previous gastric resection or lap band dysphagia, short-gut syndrome, gastroparesis, or other conditions that limit the ingestion or gastrointestinal absorption of drugs administered orally. Gastroesophageal reflux disease under medical treatment is allowed (assuming no drug interaction potential).
32. Have known medical history of progressive multifocal leukoencephalopathy (PML).

Test drug:

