- If no other cause is identified and the Investigator believes it is appropriate, particularly if QTcF remains elevated (after above measures have been implemented, or as determined by the Investigator), study treatment may be interrupted, and an ECG should be rechecked in approximately 1 week after the QTcF prolongation was first observed or more frequently as clinically indicated. If QTcF has recovered or improved and the Investigator believes it is safe to do so, re-challenge with study treatment should be considered if held.
- ECGs should be conducted at least weekly (eg, at every scheduled visit) for 2 weeks following QTcF reduction ≤ 480 msec.

Table (8.11.1) 1 - Management of QT Prolongation by CTCAE Grade

NCI CTCAE Grade	Management
Grade 2: QTc interval greater than 480 msec to 500 msec*	
 Monitor and supplement electrolyte levels as clinically indicated Review and adjust concomitant medications with known QTc interval-prolonging effects Interrupt ivosidenib Restart ivosidenib at 500 mg once daily after the QTc interval returns to less than or equal to 480 msec. Monitor ECGs should be conducted at least weekly for 2 weeks following resolution of QTc prolongation.
Grade 3: QTc interval greater than 500 msec*	
 Monitor and supplement electrolyte levels as clinically indicated Review and adjust concomitant medications with known QTc interval-prolonging effects. Interrupt ivosidenib. Resume ivosidenib at a reduced dose of 250 mg once daily when QTc interval returns to within 30 msec of baseline or less than or equal to 480 msec. Monitor ECGs at least weekly for 2 weeks following resolution of QTc prolongation. Consider re-escalating the dose of ivosidenib to 500 mg daily if an alternative etiology for QTc prolongation can be identified.
Grade 4: QTc interval prolongation with signs/symptoms of life-threatening arrhythmia	
 Discontinue ivosidenib permanently.

*Increase of 60 msec or more from baseline, without value of QTc interval greater than 480 msec as per table above does not link to IMP dose interruption or reduction.

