#### 5.4.3.2. Electrocardiogram

Descriptive statistics for the actual values and changes from baseline over time will be summarized for each ECG parameter: QT (msec), RR interval (msec) and QTcF (Fridericia's correction). QTcF is calculated as QTcF = QT/cube root of RR interval.

The proportion of subjects with maximum post-baseline absolute QTcF intervals that fall into following categories will be presented:

- $\leq 450$  msec.
- $>450$  and  $\leq 480$  msec.
- $>480$  to  $\leq 500$  msec.
- $>500$  msec.

The proportion of subjects who have a maximum post-baseline change from baseline in QTcF intervals of the following categories will be presented:

- $\leq 0$  msec.
- $>0$  to  $\leq 30$  msec.
- $>30$  to  $\leq 60$  msec.
- $>60$  msec.

A listing of subject-level ECG measurement will be provided.

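### Criterion 27 lets the Sponsor admit a prolonged QTcF with no stated upper value, which conflicts with the interruption and restart limits in the QT table; the SAP's absolute QTcF table does not separate persisting entry prolongation from new prolongation

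*Protocol*

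**What the plan says.** **Entry.** Criterion 27 appears in the protocol synopsis and in Section 5.2 with the same content. It excludes a QTcF at or above "450 msec or other factors that increase the risk of QT prolongation or arrhythmic events", and then states: "Bundle branch block and prolonged QTcF interval are permitted with approval of the Sponsor". Neither copy gives a highest value that may be approved, and no other section supplies one.

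**Management on treatment.** Table (8.11.1) 1 works by QTc level.
- Its first row is "Grade 2: QTc interval greater than 480 msec to 500 msec". The listed actions include interrupting ivosidenib and restarting it "after the QTc interval returns to less than or equal to 480 msec".
- Its second row is "Grade 3: QTc interval greater than 500 msec". Interruption is again listed, with resumption at a reduced dose "when QTc interval returns to within 30 msec of baseline or less than or equal to 480 msec".
- The footnote says that a rise of 60 msec or more, without a value above 480 msec, does not lead to interruption or reduction.

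The text of Section 8.11.1 above the table is softer. For subjects whose QTcF becomes longer than 480 msec on treatment, it leaves interruption to the Investigator's judgment when no other cause is found.

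**Analysis.** SAP 5.4.3.2 says: "The proportion of subjects with maximum post-baseline absolute QTcF intervals that fall into following categories will be presented". The categories are up to 450, above 450 to 480, above 480 to 500, and above 500 msec. The same section plans a table of maximum change from baseline (up to 0, above 0 to 30, above 30 to 60, above 60 msec) and a subject-level ECG listing. SAP 8.1.3 defines baseline as the last value before dosing.

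**The concern.** QT prolongation is named in protocol Section 2.4 as an important identified risk of ivosidenib in all indications. The entry exception can admit a subject whose QTcF already lies in a band where the management table lists interruption. Site staff would then hold a Sponsor approval to treat and a table that directs them to interrupt, with no passage saying how the table applies when the starting value is already above its threshold. An ECG is scheduled 2 hours after the first dose (Section 8.2.3), so the question could arise on Day 1. Section 8.10.1.1 adds that a subject who cannot resume within 28 days should be discontinued, subject to exemptions for clinical benefit.

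The second stake is how the safety data read. In a table of worst on-treatment QTcF with about 10 subjects, a prolongation that was present before the first dose and persisted looks the same as one that arose on drug.

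**Working it through.** The plan states no figure to reproduce on this point. The check is to run entry values through the documents' own rules. The entry values are assumptions chosen for illustration; the thresholds come from the documents.

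**Inputs**
- Exclusion from 450 msec upward, waivable, no ceiling (criterion 27).
- Grade 2 band: above 480 to 500 msec; restart at 480 msec or less (Table (8.11.1) 1).
- Grade 3 band: above 500 msec; resume within 30 msec of baseline or at 480 msec or less (same table).
- SAP categories for the absolute maximum and the maximum change (SAP 5.4.3.2).
- About 10 subjects (protocol Section 10.2).

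**Formula.** The Grade 3 resume condition is an either/or, so for baseline b the highest QTc at which it is met is max(b + 30, 480).

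| Assumed entry QTcF, unchanged on drug | Row of QT table | Grade 3 resume limit | SAP absolute category | SAP change category |
|---|---|---|---|---|
| 455 | none | max(485, 480) = 485 | >450 to 480 | ≤0 |
| 475 | none | max(505, 480) = 505 | >450 to 480 | ≤0 |
| 490 | Grade 2, interrupt | max(520, 480) = 520 | >480 to 500 | ≤0 |
| 505 | Grade 3, interrupt | max(535, 480) = 535 | >500 | ≤0 |

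**Step 1: interruption without change.** Any entry value above 480 msec that stays the same meets an interruption row.

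**Step 2: Grade 2 restart.** The limit is 480 msec regardless of baseline. For an entry value of 490 msec, the subject must fall 490 − 480 = 10 msec below the entry value before restarting.

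**Step 3: Grade 3 resumption.** If b is below 450, then b + 30 is below 480, the 480 msec limb governs, and the table is coherent. If b is above 450, then b + 30 exceeds 480, so resumption is allowed at values inside the Grade 2 interruption band. If b is above 470, then b + 30 exceeds 500 and the limit lies inside the Grade 3 band itself. At an unchanged 505 msec, the same reading meets both the interruption row and the resume condition. For b = 490, resumption is possible at up to 520 msec after a Grade 3 value (at the reduced dose the table names), but only at 480 msec or less after a Grade 2 value. The table is therefore coherent for baselines below 450 msec, and breaks for those admitted above 450 msec by the exception.

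**Step 4: SAP table.** A subject at an unchanged 490 msec is counted in the >480 to 500 row of the absolute table and in the ≤0 row of the change table. A subject at 505 msec before dosing whose highest later value is 475 msec is counted in the >450 to 480 row, so the baseline itself does not enter. One subject in 10 is 1/10 = 10% of the table.

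**Step 5: comparison within the SAP.** Baseline-to-worst shift tables are planned for laboratory grades (SAP 5.4.2) and ECOG PS (SAP 5.4.3.4). None is planned for QTcF.

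**The case against.** Several points on the other side are sound.

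- A reader might infer that the SAP counts the entry value as on-treatment prolongation. It does not. The table uses post-baseline maxima and baseline is pre-dose. The change table would show an unchanged subject as ≤0, and the ECG listing shows each value. Protocol Section 8.3.1.2 records a pre-existing condition as an adverse event only if it worsens, and Section 10.1.2.5.1 counts events that are new or worsening. What remains is a gap in one table.
- A reader might infer that the QT table ignores baseline altogether. The Grade 3 resume condition refers to it. That reference is what produces the overlap in Step 3.
- A reader might infer that the two rules can never both be followed. They act at different times, so a subject can be approved, treated, and then interrupted. That is literally possible, but the documents do not say that it is intended, and the overlapping resume limits remain.
- The Section 8.11.1 text is discretionary, so interruption is not uniformly required. This is true, but the table directly below it is directive, which is a further inconsistency.
- The exception needs case-by-case Sponsor approval, and criterion 30 lets the Investigator exclude a subject at undue risk. The sentence might also mean prolongation accompanying bundle branch block only. These narrow its use, but neither reading supplies an upper value.
- Nothing in the documents indicates that anyone will be approved above 480 msec. This stands, and it limits what can be said about frequency.

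**Conclusion.** The point holds as a conflict between stated rules for subjects admitted under the exception. Above 480 msec at entry, an unchanged value lies in an interruption band, and the Grade 2 restart limit is below the entry value. Above 450 msec at entry, the Grade 3 resume condition permits dosing inside the Grade 2 interruption band. The Section 8.11.1 text and its table also differ on whether interruption is discretionary.

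The SAP part is narrower: entry prolongation that persists after dosing is not separated from new prolongation in the absolute-category table, although the change table and the listing allow it to be traced.

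The size is conditional. The documents do not show how often the exception will be used. One such subject would be about 10% of the QTcF table, assuming about 10 treated subjects. The effect is on treatment conduct and safety description for those subjects. The exact binomial test of the primary endpoint and its error rate are unaffected.

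**What to change.** **Protocol.** Reconcile both copies of criterion 27, the Section 8.11.1 text and Table (8.11.1) 1, so that they state together how the rules apply to a subject whose QTcF is already prolonged at entry, and whether interruption is directed or discretionary. The clinical team sets the rule; this review does not propose a threshold.

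**SAP 5.4.3.2.** Add a cross-tabulation of baseline QTcF category by worst post-baseline QTcF category, using the existing absolute categories, and flag subjects enrolled under the exception in that table and in the ECG listing.

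**Cost.** A clause or footnote in the protocol passages, through the usual amendment route, and one added table plus a flag in the SAP outputs. The ECG values are already collected at screening and on treatment, so no new data are needed.

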CSR	Clinical study report
CT	Computed tomography
CYP	Cytochrome P450
DDI	Drug-drug interaction
DME	Drug-metabolizing enzyme
DNA	Deoxyribonucleic acid
DOR	Duration of response
ECG	Electrocardiogram
ECHO	Echocardiography
ECOG	Eastern Cooperative Oncology Group
eCRF	Electronic case report form
EDC	Electronic data capture
EORTC-QLQ-BIL21	European Organisation for Research and Treatment of Cancer - Quality Of Life Questionnaire - Cholangiocarcinoma and Gallbladder Cancer Module
EORTC-QLQ-C30	European Organisation for Research and Treatment of Cancer - Quality Of Life Questionnaire – Core Questionnaire
EOT	End of treatment
EQ-5D-5L	5-level EuroQol five dimensions questionnaire
G-CSF	granulocyte colony-stimulating factor
GCP	Good Clinical Practice
GFR	Glomerular filtration rate
GLP	Good Laboratory Practice
GM-CSF	granulocyte-macrophage colony-stimulating factor
HBV, HCV	Hepatitis (B/C) virus

hCG	Human chorionic gonadotropin
HIV	Human immunodeficiency virus
HR	Hazard ratio
HRQOL	Health-related quality of life
ICH	International Council for Harmonisation
IDH, IDH1, IDH2	Isocitrate dehydrogenase protein, 1, 2
IEC	Independent Ethics Committee
IRB	Institutional Review Board
IRC	Independent Radiology Center
ITT	Intent-to-Treat
IWRS	Interactive web response system
LVEF	Left ventricular ejection fraction
MDS	myelodysplastic syndrome
MedDRA	Medical Dictionary for Regulatory Activities
MRI	Magnetic resonance imaging
mSv	Millisievert
MTD	Maximum tolerated dose
NCI CTCAE	National Cancer Institute Common Terminology Criteria for Adverse Events
NYHA	New York Heart Association
OR	Objective Response
OS	Overall survival
PAS	Pharmacokinetic analysis set
PD	Pharmacodynamic
PFS	Progression-free survival
P-gp	P-glycoprotein
PI	Principal Investigator Designated Co-Investigator can act tasks on behalf of Principal Investigator to the extent permitted by GCP.
PK	Pharmacokinetic
PPS	Per protocol set
PR	Partial response
PS	Performance status
QALYs	quality-adjusted life years
QD	Once daily
QTcB, QTcF	Heart-rate corrected QT interval (using Bazett's / Fridericia's formula)
R/R	relapse or refractory
RECIST	Response Evaluation Criteria in Solid Tumors
RPSFT	rank-preserving structural failure time
SAE	Serious adverse event
SAP	Statistical analysis plan
SAS	Safety Analysis Set
SD	Stable disease
Signed	Signed or print name and sealed
$t_{1/2}$	Elimination half-life
TEAE	Treatment-emergent adverse event
TTR	Time to response
ULN	Upper limit of normal
WOCBP	women of child bearing potential

1. ADMINISTRATIVE STRUCTURE OF THE STUDY

Non-Sponsor parties, Sponsor parties and contract research organizations responsible for local management of the study are described in a separate document entitled: "Administrative part of clinical study protocol."

The list of Investigators is given in a separate document.

Designated Co-Investigator can act tasks on behalf of Principal Investigator to the extent permitted by GCP.

2. BACKGROUND INFORMATION

2.1. Cellular Metabolism and Cancer

[figure not shown]
2.1.1. The Role of Isocitrate Dehydrogenase

The isocitrate dehydrogenase (IDH) proteins are critical metabolic enzymes that exist as 3 isoforms: IDH1, IDH2, and IDH3 ([Figure \(2.1.1\) 1](#)). All 3 catalyze the oxidative decarboxylation of isocitrate to produce carbon dioxide (CO₂) and alpha-ketoglutarate (α-KG). IDH1 and IDH2 produce adenine dinucleotide phosphate (NADPH) whereas IDH3 only produces NADH.

Cancer-associated mutations have been identified in IDH1 and IDH2; however to date, no mutations have been described in IDH3 ([Yen et al, 2010](#)). One fundamental difference between IDH1 and IDH2 is the subcellular localization of the 2 proteins. IDH1 is localized in both peroxisomes and cytosol. ([Geisbrecht and Gould, 1999](#); [Yoshihara et al, 2001](#)) IDH2 is a mitochondrial isoform of IDH. ([Wang et al, 2013](#); [Yoshihara et al, 2001](#)).

The genes encoding IDH1 and IDH2 are located on chromosome 2q33.3 and 15q26.1, respectively. Mutations in these IDH proteins most commonly lead to alterations affecting arginine-132 (R132H or R132C) in IDH1, and the analogous arginine residue (arginine-172 mutated to lysine [R172K]) or arginine-140 (R140Q) in IDH2.

Figure (2.1.1) 1 - The Citric Acid Cycle

Abbreviations: CO_2 = carbon dioxide; IDH = isocitrate dehydrogenase; NADH = nicotinamide adenine dinucleotide; NADPH = nicotinamide adenine dinucleotide phosphate; α KG = alpha-ketoglutarate.

2.1.2. Tumorigenesis Hypothesis

Mutant IDH1 and IDH2 are not catalytically inactive enzymes, but rather possess novel enzymatic activities, consistent with a gain-of-function, reconciling the heterozygous nature of the point mutations (Dang *et al*, 2009). The mutated proteins themselves have a gain of- function, neomorphic- activity, catalyzing the reduction of α -KG to 2hydroxyglutarate (2-HG) (Dang *et al*, 2009). The Sponsor's studies established that purified mutant protein efficiently catalyzes the proposed reduction of α -KG to 2-HG, while being unable to synthesize isocitrate (Dang *et al*, 2009). Mutations in IDH1 and IDH2 are almost always mutually exclusive and occur at very early stages of tumor development suggesting that they promote formation and progression of tumors (Welch *et al*, 2012).

Evidence supports that cancer-associated IDH mutations block normal cellular differentiation and promote tumorigenesis via the abnormal production of 2-HG, a potential oncometabolite. High levels of 2-HG have been shown to inhibit α -KG-dependent dioxygenases including histone and deoxyribonucleotide demethylases, which play a key role in regulating the epigenetic state of cells. (Chowdhury *et al*, 2011; Koivunen *et al*, 2012; Xu *et al*, 2011). Consistent with 2-HG promoting tumorigenesis via an effect on chromatin structure, subjects with IDH mutations display a cytosine-guanine dinucleotide (CpG) island methylator phenotype (CIMP) and several studies have shown that overexpression of IDH mutant enzymes can induce histone and deoxyribonucleic acid (DNA) hypermethylation as well as impair normal cellular differentiation (Lu *et al*, 2012; Turcan *et al*, 2012) (Figueroa *et al*, 2010).

Clinical studies in several tumor types including glioma and acute myelogenous leukemia (AML) have found elevated levels of 2-HG in cells with mutant IDH1 and IDH2 as compared to cells with wild-type alleles (Gross *et al*, 2010; Ward *et al*, 2010). In normal cells, 2-HG is present in low levels. However, IDH1/IDH2 mutations in cancer cells result in the excess accumulation of 2-HG to extremely high levels, which can alter a number of downstream cellular activities. The elevated levels of 2-HG also are present in the sera and urine of some affected subjects.

2.2. Overview of Cholangiocarcinoma

Cholangiocarcinomas (CCAs) are rare cancers (accounting for 3% of all gastrointestinal malignancies) that arise from biliary epithelium and are typically diagnosed at advanced stages for which curative surgery is not feasible. The classification of CCAs is divided anatomically as extrahepatic, intrahepatic (iCCA), and perihilar (Saha *et al*, 2014; Van Dyke *et al*, 2019). The disease is often advanced and incurable at the time of diagnosis. Common presentation includes symptoms related to biliary tract obstruction including jaundice, abdominal pain, weight loss, fever, fatigue, and abnormal liver function tests. The prognosis for subjects with CCA is poor; regardless of stage at diagnosis, the 5-year survival rates associated with both intrahepatic (iCCA) and extrahepatic CCA are 9% to 10% and only 2% in subjects with distant metastases (ACS, 2021). CCA (intrahepatic and extrahepatic) affects approximately 8,000 people in the US annually (ACS, 2019) and approximately 1.3 in 10,000 people in the EU (Agency, 2018). According to the 21st National Primary Liver Cancer Follow-up Survey (published in 2020), in which 546 major centers in Japan participated, which provides the latest incidence information, the number of iCCA cases obtained over 2 years was 1,332 (equivalent to 666 cases/year) and accounted for 6% of the primary liver cancer cases. National cancer statistics show 38,312 cases of primary liver cancer, and if we assume that 6% of these cases are iCCA, the annual number of subjects is 2,298 (Matsuda, 2018).

The most recent Japanese prospective study showed that the IDH1 mutation positivity rate by comprehensive genetic testing was 3% (2/66) for intrahepatic biliary tract cancer (Okawa, 2021).

As early-stage disease is commonly asymptomatic, only a minority of CCA subjects are diagnosed with resectable disease, while most of the subjects present with locally nonresectable or metastatic disease (Rizzo *et al*, 2021). The first-line and only approved standard-of-care treatment for subjects with CCA, including subjects with IDH1 mutation-positive CCA, in the locally nonresectable or metastatic setting is the combination of durvalumab with gemcitabine/cisplatin. This approval was granted in 2022 in both the US and EU and was based on the Phase 3 TOPAZ-1 trial evaluating the durvalumab and gemcitabine/cisplatin combination vs gemcitabine/cisplatin. The addition of durvalumab resulted in improved OS of 12.8 months compared with gemcitabine/cisplatin OS of 11.5 months (hazard ratio [HR] 0.80, confidence interval [CI] 0.66-0.97, $p = 0.021$) (Oh *et al*, 2022).

Second-line chemotherapy regimens produce an incrementally smaller therapeutic benefit, with an average median PFS of 2 to 3 months (Brieau *et al*, 2015; Lamarca *et al*, 2021). Overall survival outcomes are also limited to approximately 6 months (Kim *et al*, 2017; Lamarca *et al*, 2021; Matsuyama *et al*, 2018; Ying and Chen, 2019) demonstrating the need for novel treatment options in subjects with CCA.

